Primary research question: Compared to a fully automated virtual (with a workbook or online material) intervention, what is the effect of the virtual intervention with telephone support for pregnant women with subclinical depressive symptoms on maternal depression at 3 months' postpartum? We adopted an indicated prevention strategy (targeted or secondary prevention), targeting women with symptoms of depression during pregnancy.

Secondary research questions: Compared to a fully automated virtual (with a workbook or online material) intervention, what is the effect of the virtual intervention with telephone support on: 1) maternal depression at 6 months' postpartum; 2) maternal anxiety, perceived stress, well-being, self-efficacy, self-compassion, sleep quality, tobacco, alcohol and drug usage, social functioning, social support, marital satisfaction, co-parenting and parental cognitions and practices, at 3 and 6 months' postpartum; 3) child's socioemotional development at ages 3 and 6 months; 4) maternal health care services utilization at 6 months' postpartum.

Tertiary research questions: What is the effect of a virtual intervention (with a workbook or online material) + telephone support on 1) partner depression, anxiety, perceived stress, well-being, self-efficacy, self-compassion, sleep quality, tobacco, alcohol and drug usage, social functioning, social support, marital satisfaction, co-parenting and parental cognitions and practices, at 3 and 6 months' postpartum; 2) What are the moderators of the effect (e.g., compliance to the intervention, COVID-19 infection of self or relatives, personality disorder traits, socioeconomic level, ethnicity, gender at the baseline, and sex of the child).

Method

[figure not shown]
Design

A randomized controlled trial (RCT) of 500 Quebec women with a 1:1 assignment to either virtual preventive intervention with telephone support or without telephone support (control). Figure 1 presents the trial design.

Population

French-speaking pregnant women older than 14 years old, with subclinical levels of depression (EPDS 9-12).

Figure 1. Trial design

Pregnant Women Recruitment

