Sample size. A meta-analysis of 58 studies indicates that the overall prevalence of postpartum depression is 17% (95% CI: 0.15–0.20) (53). This estimate falls within previously published estimates of 13%–19.2% (54, 55) and is similar to Hahn-Holbrook's 2018 finding of 17.7%. In-person interventions using the *Mother & Babies* course reported moderate effect sizes (OR = 0.28 (0.08-0.94) (22) and OR = 0.45 (0.19-1.10) (24)). Fully web-based without nurse-based telephone support reported small to moderate effect sizes (40). Given that the proposed intervention is offered virtually with nurse-based telephone support, we calculated a sample size that allows us to detect a moderate decrease in rates of clinical depression. We anticipate that 20% of pregnant women in the control group will have an EPDS score ≥ 13 at postpartum. A total of 500 pregnant women (250 per arm) is needed to detect an absolute reduction of 10% (i.e., 20% of women with EPDS ≥ 13 in the control arm versus 10% in the intervention arm) with 80% of power and a 2-tailed alpha of 5%. The sample size includes an attrition rate of 10% for 3 months' postpartum and another 10% between 3 and 6 months' postpartum. Based on our experience with pregnant women and the intervention (see Section about Pilot Study), the 10% attrition estimate is conservative. As most of the secondary

outcomes are continuous, the sample size provides enough power to detect small to moderate effect sizes using a 2-tailed alpha of 1% to account for multiple tests.

Compliance. We conducted a feasibility pilot study including 17 pregnant women. All began to read the online material and 2 refused further participation after 2 telephone calls, a dropout rate of 11.7%. We therefore expect that 80-90% of the intervention group will read at least some of the intervention material. Intervention compliance will be defined as completion of a minimum of 6/8 online modules and 6/10 telephone follow-ups. Compliance will be monitored automatically online and by nurses during telephone calls. Weekly text reminders will be sent out to maximize compliance (see details in Appendix H).

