Duration of treatment period. The typical duration of the program is 2 months (8 weeks) during pregnancy and 2 months over the first 3 months of the baby's life. The two postpartum sessions aim to lend support during the challenges of the postpartum period. The proposed frequency of nurse telephone follow-up is once/week in pregnancy and once/month in postpartum, but this can be adapted to the needs of the woman and/or her partner. Figure 3 presents the intervention and assessments.

Figure 3. Frequency and duration of the follow-up

Participants will fill out questionnaires (online or by telephone) at T₀ (12-25 weeks' gestation), T₁ (3 months' postpartum), and T₂ (6-months postpartum) to assess baseline values and trial outcomes, respectively. If we show efficacy at 3 months' postpartum (primary outcome), we will seek funding to follow families over the early childhood years. Real date of birth will be assessed six weeks after the estimated date of birth.

Coaches training and supervision. PhD students in clinical psychology and Master's students in nursing are ideally suited to conduct the 10 follow-up calls. They will be supervised by our multidisciplinary team (2 nurses, 2 clinical psychologists, and 2 psychiatrists). All coaches will receive 5-day training in perinatal mental health and use of the intervention material. Procedures for calls will be outlined in the intervention manual. The supervision team will oversee implementation as part of the Executive Committee. Intervention sessions will be audiotaped and randomly reviewed by the supervision team to ensure compliance with the material.

Virtual intervention without telephone support (control group). The control group will receive a fully automated version of the virtual intervention

Data Collection

We will conduct a comprehensive assessment of perinatal maternal mental health and functioning as well as factors that may modify the impact of the intervention. The chosen assessment tools are validated (French and English), require low levels of literacy and take only 15-30 minutes to complete (Appendix L, Description of assessment tools). They have been used previously with pregnant women and examined for clarity, comprehension, and ease of use. The questionnaires will be completed online via REDCap or over the telephone with a research assistant blinded to group allocation depending on maternal preference, and with the partner if the woman so chooses.

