
support or attachment, social integration, reassurance of worth, tangible help, orientation, and opportunity for nurturance (96, 97).

Parent and child assessments. Maternal depression has repeatedly been associated with poorer quality mother-infant relationships, attachment, and child-emotional development. **Parenting** will be assessed at 6 months postpartum with the Parent's Cognition and Conduct Toward the Infant Scale (ÉCOPAN) (98). **Child social, emotional and cognitive development.** The Ages and Stages Questionnaire 3rd edition (ASQ-3) is a widely used parent-reported scale covering physical, social, emotional, and cognitive child development at ages one month to 5 ½ years. Its parent-centric approach and inherent ease of use have made it the most widely used developmental screener in the world (99). **Child difficult temper** will be evaluated at 6 months postpartum with the Infant Characteristics Questionnaire (ICQ) (100, 101).

Other variables (effect modifiers). **Compliance to the intervention.** Participant and partner use will be calculated automatically using web-based statistics and the number of modules completed will be self-reported. The number of calls with the nurses will also be recorded. **Intervention Team Activity Log.** All intervention activities (telephone discussions, voice messages, missed sessions) will be documented. **Personality disorders symptoms.** These may be important modifiers of the intervention and thereby impact compliance. We will use the 25-item Personality Inventory for DSM-5 Brief Form (PID-5 BF) (102). Groups will be created using a 30% cut-off score for each subscale. **Gender roles.** Using data at T₂ we will create a gender role score for participants and partners by identifying gender-related variables such as employment status, income; gender roles assessed using the Bem Sex Role Inventory (BSRI) (103, 104). Sex of the child will also be tested as a potential effect modifier. **The sociodemographic and medical history.** Information will be collected about the household, employment status, revenue, education level, ethnicity, reproductive history, COVID-19 infection history and weight.

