Economic evaluation. Service utilization will be measured using a slightly modified version of the **Health Service Utilization and Cost of Care Questionnaire** (105) to assess childcare expenses and travel costs incurred by patients to obtain care. Costs of administering the intervention include a) recruiting and training of nurses, b) nurses' time to provide the intervention, and c) supervision of nurses.

Planned Analyses

Data will be analyzed using SAS software using an intent-to-treat approach. A two-sided significance level of 0.05 will be used for the primary outcome; a significance level of 0.01 (two-sided) will be used for secondary and other outcomes to account for multiple outcomes. Demographic and other baseline variables will be compared between study groups using descriptive statistics (mean, standard deviation, proportions).

For the primary outcome, a two-sample sided test of proportion (chi-square test) will be used to compare the difference in the proportion of women with EPDS in the clinical range (> 13) at 3 months' postpartum. The same approach will be used for the 6-month assessment (secondary outcome). These analyses will be supplemented by an analysis using EPDS scores, where the baseline EPDS score will be used as covariate in an ANCOVA model including the 3- and 6-month EPDS scores. With this model, we will obtain 95% confidence intervals of EPDS score differences between intervention arms at 3 and 6 months' postpartum. Sensitivity analyses will be performed to investigate the potential bias introduced

by attrition. A method based on inverse-probability-of-attrition weights (IPAWs) will be used (101, 102).

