For secondary outcomes, the statistical method for comparing intervention arms will depend on the distribution of the outcome variable. For binary variables, chi-square tests will be used. The corresponding 95% CI for the difference in proportions will also be provided. In the unlikely event that randomized intervention arms are unbalanced for baseline variables known to be associated with primary and secondary outcomes, logistic regression will be used where unbalanced variables will be included. For continuous variables, we will use ANCOVA models as described above. Again, unbalanced variables will be added if needed. If the intervention is found to be effective, exploratory analyses will be conducted to explore the potential effect of moderator variables using causal inference models including gender and intervention compliance (103, 104). No formal interim efficacy analysis is planned. Ethical practices and conduct of the trial as well as all safety concerns will be reported to an independent Data and Safety Monitoring Committee.

Planned subgroup analyses. The ANCOVA models presented above will be expanded to include the socioeconomic status of the participant, ethnicity, personality disorder symptoms subgroup variable as well as interaction with the intervention.

Pilot Study

We conducted a feasibility study to assess acceptability and compliance to the intervention (n = 17). Pilot data indicate that women used a mix of electronic devices to access the intervention. All used an iPad at some time, 40% also used their smartphone and 20% also used a computer. Telephone follow-up by a nurse was rated as “essential” (40%), “very useful” (40%), or “useful” (20%). Online sessions were rated as “very useful” (60%) or “useful” (40%). Strategies proposed in the intervention (cognitive restructuring, relaxation, behavioral modification, social support) were used “regularly” (30%), “often” (50%), “occasionally” (10%), or “never” (10%). The material was rated as “very easy to understand” (90%) or “easy” (10%). Each strategy was used at least occasionally by 86% of women. Qualitative data indicated high levels of appreciation (Appendix A).

Ethical considerations

Voluntary informed consent

The recruiting process will allow women to give a voluntary informed consent (Appendix E). The consent form will be signed on the online platform provided by the URCA.

Confidentiality and Privacy Protection

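### Compliance requires calls that only one arm is offered, so it cannot be estimated as a moderator of the arm effect, and it is a poor exposure for a complier analysis

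*Combined protocol and SAP*

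**What the plan says.** The Compliance paragraph under Sample gives the only definition in the document: "Intervention compliance will be defined as completion of a minimum of 6/8 online modules and 6/10 telephone follow-ups". Both conditions must be met.

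The arms differ in telephone support only (Design). Of the comparator the protocol says: "The control group will receive a fully automated version of the virtual intervention". The description of the Parents and Babies intervention gives encouraging the use of the online material as the first aim of the coaching calls.

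Compliance is given the role of effect modifier in three places:

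- The tertiary questions under Research Questions ask: "What are the moderators of the effect (e.g., compliance to the intervention" (first in a list of examples).
- Other variables (effect modifiers) lists compliance first. It combines automatic web statistics with self-report ("the number of modules completed will be self-reported") and a record of the number of calls.
- Planned Analyses says that "exploratory analyses will be conducted to explore the potential effect of moderator variables using causal inference models including gender and intervention compliance". This applies only under the condition "If the intervention is found to be effective".

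No estimand, estimator, identifying assumption or control-arm version of compliance is given. The main analysis is separate: "Data will be analyzed using SAS software using an intent-to-treat approach".

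**The concern.** The trial asks what telephone support adds to a programme that both arms receive. The compliance rule joins the randomised component (calls) to a component available to everyone (modules). Three difficulties follow.

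First, a moderator must be able to take more than one value in each arm. This one is fixed at non-compliant for every control.

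Second, compliance arises after randomisation, and its module half is something the calls are meant to change. It may lie on the pathway of the effect, which makes it a possible mediator and not a modifier.

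Third, if the binary rule is used as treatment received, a woman with ten calls and five modules is classed with women who took no call at all.

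At stake is whether the tertiary question on compliance can be answered, and whether any compliance-adjusted effect in the report can be interpreted.

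**Working it through.** **Plan figure used.** The only plan figure needed is the assumed 10-point difference (20% against 10%, Sample size). It fits the stated total. With pooled variance, n per arm = [1.96·√(2·0.15·0.85) + 0.8416·√(0.20·0.80 + 0.10·0.90)]² / 0.10² = (0.9897 + 0.4208)² / 0.01 = 199. Then 199/0.80 = 249 per arm, or 498 in total, against the stated 500. That figure is not in dispute.

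**Step 1: compliance as moderator.** Let Z be arm (1 = telephone) and C the composite. The interaction model has linear predictor b0 + b1·Z + b2·C + b3·Z·C. Every control has C = 0, so C and Z·C are the same column. Only b2 + b3 can be estimated; b3, the moderation, cannot. The sum compares compliers with non-compliers inside the telephone arm, which is not a randomised comparison.

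**Step 2: compliance as exposure in a complier analysis.** With arm as instrument and no compliance in controls, the estimate is D/c, where D is the intent-to-treat difference and c the compliant fraction of the telephone arm. The documents give no value for c; the only uptake forecast (80-90%) concerns reading at least some of the material. Over an assumed range, with D = 10 points:

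- c = 90%: 11.1 points
- c = 80%: 12.5
- c = 70%: 14.3
- c = 60%: 16.7
- c = 50%: 20.0
- c = 40%: 25.0

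D/c is the effect in compliers only if assignment does nothing for women outside the composite.

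**Step 3: what happens if it does something.** Assumed telephone arm: 50% meet both thresholds, 20% take at least 6 calls but complete fewer than 6 modules, 20% take 1 to 5 calls, 10% take none. Assumed benefit: 10 points with at least 6 calls, 5 points with 1 to 5 calls, 0 with none.

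- D = 0.5·10 + 0.2·10 + 0.2·5 = 8.0 points.
- Composite as exposure: 8.0/0.50 = 16.0, against a true 10.0 in those women.
- At least 6 calls as exposure: 8.0/0.70 = 11.4, against a true 10.0.
- Any call as exposure: 8.0/0.90 = 8.9, equal to the true average in women who took any call.

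If women outside the composite gain nothing, D = 0.5·10 = 5.0 and the composite gives 5.0/0.50 = 10.0, which is correct. The bias therefore comes from benefit among women classed as unexposed.

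**Step 4: other models.** Keep the Step 3 fractions and benefits, and let untreated risk differ between compliers and the rest, with control risk 20% throughout.

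- Compliers at lower risk (16% against 24%): treated compliers have 16 − 10 = 6%. Per-protocol, compliers against all controls: 20 − 6 = 14.0. As-treated: everyone else averages [20 + (0.5·24 − 3)]/1.5 = 19.3%, giving 13.3.
- Compliers at higher risk (24% against 16%): treated compliers have 24 − 10 = 14%. Per-protocol: 20 − 14 = 6.0. As-treated: [20 + (0.5·16 − 3)]/1.5 = 16.7%, giving 2.7.

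The 3 subtracted is the benefit outside the composite, 0.2·10 + 0.2·5. Against a true 10.0, these models run from 2.7 to 14.0.

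**The case against.** A reader might infer that the planned analysis will overstate the effect of telephone support. The documents do not support that as a general statement. Planned Analyses names no estimator, and nothing there says that the intent-to-treat difference will be divided by the joint compliant fraction. The direction depends on the model and on who complies (Step 4), and even a complier estimate is unbiased if women outside the composite gain nothing (Step 3).

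Nor is zero compliance among controls a bias in itself. One-sided non-compliance is the usual setting for a complier analysis, and the calls are assigned by randomisation. The fault lies in the module condition and the call threshold.

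It would also be too strong to say that the trial cannot show whether calls raise module use. Module counts and web use are recorded without restriction by arm; the comparison is simply not pre-specified.

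It is fair to add that the binary rule sits in a paragraph on uptake, that the effect-modifier section lists modules and calls separately, and that a joint rule describes adherence to the whole package sensibly. The link from the rule to the causal models is therefore an inference. But it is the only definition of compliance in the document, and no other is offered for the analysis. The citations do not settle the matter: the numbers given for the causal models lead to sex-role inventory references, while papers on non-compliance and on causal estimands stand a few entries later.

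Applying only the module half to controls would be a possible rescue. The plan does not say so, and complier would then mean different things in the two arms.

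Finally, the stakes are limited. This work is exploratory, tertiary and conditional on a positive result.

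**Conclusion.** The point stands in a limited form. Under the only definition given, no control can comply, so compliance cannot be estimated as a moderator of the arm effect. That holds whatever compliance rate is observed. Because the calls may change module completion, the composite is also partly an outcome of assignment.

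Used as exposure in a complier analysis, the composite breaks the exclusion assumption whenever women below either threshold are affected by their calls, and it overstates the effect if they benefit. The size cannot be fixed from the documents. The 16.0 against 10.0 rests wholly on the fractions and benefits assumed in Step 3, and the direction is open under other models. The primary test and the other intent-to-treat comparisons are untouched. This is worth correcting before analysis, but it does not threaten the main result.

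**What to change.** Four changes of wording in the analysis plan:

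1. Remove compliance from the moderators in Research Questions, Other variables and Planned Analyses.
2. For any causal compliance analysis, define exposure by coaching calls received, with randomised arm as instrument. Use any call versus none as the main exposure, because it leaves no called woman classed as unexposed. Use the number of calls (0 to 10; 0 in controls) as a sensitivity analysis. Do not count retention calls or the nurse safety call under Risks to Participants, which can occur in either arm.
3. Name the estimand (the average effect in women who take at least one call), the estimator, and the assumption that assignment acts only through calls.
4. Define module completion separately, with the same threshold and data source in both arms, and report it as a between-arm comparison. The source must not depend on the coaching calls, which exist in one arm only. The Compliance paragraph counts 8 modules and the programme description 10; these must be reconciled before the threshold is set.

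The 6-and-6 rule can stay as a description of adherence in the telephone arm. No new data are needed, as calls and module use are already recorded. The cost is slightly more analysis work. The any-call effect averages over women with few and many calls, and the per-call version depends on a linear dose response.

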Loss to follow up. The following proactive telephone strategies will be employed to encourage retention. Each computer-based questionnaire will contain a contact form for the research nurse to record the date, time of the call, the status of calls (busy, call back, no answer, etc.), email address, name and contact information of the partner and of one additional reference person (e.g., family member). Participants will be telephoned during their stated “best time to contact” period. Congratulations cards will be sent at the birth of the child, showing contact information for the study. Participants will be invited to go to the study Facebook page, with periodic lotteries of gift certificates. Additional strategies to ensure a high retention rate, based on a Cochrane review (56), include card pre-notification of impending interview and a small token of appreciation for each assessment completed. All these strategies have been successfully used in [name]’ postpartum depression prevention trial with good results (retention rate = 87% of the 12-week assessment and 85% of the 24-week assessment).

Description of “Parents and Babies” (« *Toi, Moi, Bébé* ») intervention

The *Parents & Babies* intervention to be evaluated is an adaptation of the existing, evidence-based *Mothers & Babies* program (see Authorship Rights, Appendix I), which has shown efficacy in four clinical trials for the prevention of postpartum depression through in-person (group or individual) counseling (22-25). In a study with a low uptake of the intervention, a Spanish web-based format without telephone contact was tested and suggested some impact on women with moderately high levels of depression (57).

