Primary outcome. Maternal depression at 3 months' postpartum was chosen as the primary outcome to: 1) ensure comparability to other perinatal trials (60-67) and 2) to reduce potential biases induced by attrition. The primary outcome will be the proportion of women with EPDS scores above the clinical cut-off for depression (EPDS \geq 13)). Differences between experimental and control groups will be analyzed at T₁ (3 months' postpartum) and again at T₂ (6 months' postpartum, secondary outcomes). The EPDS is an internationally recommended 10-item self-report scale that assesses depressive symptoms on a 4-point scale; scores range from 0 to 30 with higher scores representing higher symptomatology. More than 80% of perinatal depression studies use self-report measures (73) and the majority use the EPDS. The EPDS was created to counter the limitations of other well-established depression scales when used during the perinatal period. It has been validated by standardized psychiatric interviews with large sample sizes and has well-documented reliability and validity of over 11 languages (50, 74). Participants will fill out the EPDS at 3 assessment times: baseline (T₀, as part of inclusion criterion), T₁, and T₂.

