Secondary outcomes. Participant and partner assessments at baseline, T₁ and T₂. The proposed intervention is based on CBT principles used to treat both anxiety and depression. As anxiety is highly correlated with perinatal depression, it is an important secondary outcome. **Generalized anxiety.** The proposed intervention is based on CBT principles used to treat both anxiety and depression. As anxiety is highly correlated with perinatal depression, it is an important secondary outcome. Anxiety will be assessed at all 3 time points, using the Generalized Anxiety Disorder 7-item (GAD-7) scale, an extensively validated self-report instrument (75-77). **Anxiety related to pregnancy** will be measured with the 10-item Pregnancy-specific anxiety scale (PRAQ-R2) (78, 79) at baseline. **Stress** will be assessed using the 10-item form of the Perceived Stress Scale, at six months postpartum (80, 81). **Well Being** will be evaluated with the 5-item WHO-5 well-being index at T₁ (82). **Self-efficacy** will be assessed using the 10-item General Self-Efficacy Scale (GSE) at 3 months postpartum (83, 84). **Self-Compassion** will be measured with the 12-item shortened version of the Self-Compassion Scale (SCS) (85-87), at 3 months postpartum. **Sleep.** Sleep may improve as a result of the increased capacity for relaxation, mindfulness, and emotional regulation fostered by the intervention. At 3 months postpartum, we will assess sleep quality, a critical aspect of perinatal maternal health, using the 19-item Pittsburgh Sleep Quality Index (PSQI) (88, 89), a self-report over a one-month interval with very good psychometric properties and validated for use during postpartum (90). **Tobacco, alcohol and drug use** will be self-reported at baseline and 3 months postpartum. **Social Adjustment** will be assessed using the 14-item screener version of the Social Adjustment Scale – Self-report (SAS-SR) (91, 92). Six major areas are covered: work (paid or unpaid), social and leisure activities, relationships with extended family, role as marital partner, role as a parent, and role within the family unit (including perceptions about economic functioning). For this study, we will only use the work subscale at 3 months postpartum. **Marital satisfaction** will be evaluated with the short version of the Dyadic Adjustment Scale (DAS-7) (93-95) at 3 months postpartum. **Co-parenting.** The proposed intervention is partner-inclusive and, as such, may improve co-parenting quality (the extent to which parents work together and agree on childcare and education). We will use a brief 14-item version of the Coparenting Relationship Scale (75) (e.g., partner pays a great deal of attention to our child; partner appreciates how hard I work at being a good parent) at 3 months postpartum. **Social Support** will be assessed at 6 months postpartum using the 10-item Social Provisions Scale (SPS-10) on emotional

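### No EPDS-only contact is described for women who do not complete the 3-month questionnaire, although the primary endpoint needs only those 10 items

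*Combined protocol and SAP*

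**What the plan says.** Under Primary outcome, the endpoint is the proportion of women at or above 13 on the EPDS at 3 months (T1). The EPDS is a "10-item self-report scale that assesses depressive symptoms on a 4-point scale". The same section gives limiting attrition bias as one reason for choosing 3 months.

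Under Data Collection, the tools "require low levels of literacy and take only 15-30 minutes to complete". They are completed in REDCap or by telephone with a blinded research assistant. The time is given for the tools as a set, not for T1 in particular.

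Under Loss to follow up, "The following proactive telephone strategies will be employed to encourage retention". The list covers calls at preferred times, call-status records, contact persons, birth cards, pre-notification, lotteries and a token per completed assessment. These measures are credited to an earlier trial with "retention rate = 87% of the 12-week assessment".

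Under Sample size, "The sample size includes an attrition rate of 10"% to 3 months, with a further 10% between 3 and 6 months.

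Under Planned Analyses, the primary test is a chi-square test by intention to treat, with no stated rule for a missing EPDS. "Sensitivity analyses will be performed to investigate the potential bias introduced" by attrition, using inverse-probability-of-attrition weights.

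**The concern.** The primary endpoint takes 10 items, while the T1 assessment is several times longer. A mother of a 3-month-old may decline the full set and still be willing to answer 10 questions. The retention measures all encourage response; none reduces the task to the one scale that the primary analysis needs.

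At stake is missing primary data that may be neither random nor equal between arms. The protocol's own review of virtual interventions suggests that high attrition in a fully automated programme may come from the lack of personal contact, and here the fully automated programme is the control arm. Depressed mothers are also plausible non-responders. Attrition weights correct only for recorded predictors of loss, not for loss that depends on the unseen 3-month score. For each woman whose EPDS is actually obtained, no such assumption is needed.

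**Working it through.** **Items at T1** (Primary outcome and Secondary outcomes; scales whose length is stated or is part of their name):

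EPDS 10 + GAD-7 7 + WHO-5 5 + GSE 10 + SCS 12 + PSQI 19 + DAS-7 7 + co-parenting 14 = 84.

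The EPDS share is 10/84 = 12%. Substance-use questions and the social-adjustment work items are additional, as would be any child form at 3 months (the secondary research questions include child development at that age).

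**Reproducing the plan's sample size.** Inputs from Sample size: 20% v 10%, two-sided 5%, 80% power, 1:1.

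n per arm = [1.96·√(2·0.15·0.85) + 0.84·√(0.20·0.80 + 0.10·0.90)]² / 0.10² = 199.

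- With 20% total loss: 199/0.80 = 249 per arm, 498 in total.
- With 0.9 × 0.9 = 81% retained: 199/0.81 = 246 per arm, 492 in total.

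Both agree with the stated 500 to within 3%, so the sample already carries about 20% loss.

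**Power at 3 months** (same formula solved for power):

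| Evaluable per arm | Corresponds to | Power |
|---|---|---|
| 200 | 20% loss | 80.2% |
| 217.5 | 13% loss (100 − 87) | 83.4% |
| 225 | 10% loss (planned) | 84.6% |
| 233 | one third of 25 recovered | 85.8% |
| 237 | one half of 25 recovered | 86.4% |

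The recovery fractions are assumptions; the documents give none.

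**Bias.** Let p be an arm's true rate, m its loss, and k the ratio of the rate among lost women to p. Then observed rate = (p − m·k·p)/(1 − m). Assume true rates of 20% v 10%, with loss of 13% in controls (the cited trial's figure) and 10% in the telephone arm (the planned figure).

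For k = 2:

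- Control: (0.20 − 0.13·0.40)/0.87 = 17.0%.
- Telephone: (0.10 − 0.10·0.20)/0.90 = 8.9%.
- Difference: 8.1 points instead of 10.

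If a random half of the lost women is recovered, m becomes 6.5% and 5%:

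- Control: (0.20 − 0.065·0.40)/0.935 = 18.6%.
- Telephone: (0.10 − 0.05·0.20)/0.95 = 9.5%.
- Difference: 9.1 points.

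| k | No recovery | Random half recovered | Recovered women like completers |
|---|---|---|---|
| 1.5 | 9.1 | 9.6 | 9.1 |
| 2 | 8.1 | 9.1 | 8.1 |
| 3 | 6.2 | 8.3 | 6.2 |

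The last column is the lower bound on the gain. If recovered women have the completers' rates, the observed rates do not move.

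Unequal loss is not required for some attenuation. With 10% loss in both arms and k = 2, the observed rates are 17.8% v 8.9%, a difference of 8.9 points.

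**The case against.** The strongest case against is that the documents show no error.

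- A reader might infer that the EPDS can be answered only inside the full set, and that any woman who does not finish it drops out of the primary analysis. The documents support neither. They do not say where the EPDS comes or that partial questionnaires are discarded. A woman who answers the EPDS and then stops may already count. Appendices E and L may settle both points. This objection stands.
- A reader might also infer that attrition is dealt with only afterwards, by weighting. That is wrong: Loss to follow up is a prevention plan, and Data Collection adds choice of mode.
- No document links loss to questionnaire length. The tools are described as easy to use, and the protocol's explanation of attrition concerns lack of personal contact. Some lost women will be unreachable or withdrawn, and a shorter form will not recover them. This stands, and it is why the recovery fractions are only illustrative.
- Power is not threatened. It stays above 80% until loss reaches about 20%.

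What remains is that no EPDS-only contact appears among the retention measures. The trial can clearly deliver one: under Pregnant Women Recruitment, the EPDS is given by telephone within a 5-minute eligibility questionnaire.

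**Conclusion.** The point holds as a cheap improvement, not as a flaw in the planned analysis. The supplied text describes no EPDS-only contact at T1 or T2, while the EPDS is 10 of at least 84 items at T1.

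The power gain is about 1 to 2 points (84.6% to about 86%), assuming one third to one half of lost women are recovered at 10% loss. The possible reduction in bias is larger but uncertain. With 13% v 10% loss and lost women at twice their arm's rate, the observed difference moves from 8.1 to 9.1 points if a random half is recovered, and not at all if those recovered resemble completers. Loss rates by arm, the rate ratio and the recovery fraction are all assumptions. The step reduces missing primary data, but women who remain unreached still need the planned sensitivity analysis.

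**What to change.** 1. In Loss to follow up, add a last step after the planned telephone contacts. A woman who has not completed the T1 (or T2) questionnaire is offered the EPDS alone, by REDCap link or by telephone with the blinded research assistant. State the number of attempts and the closing date, identical in both arms. The trigger should be these telephone contacts, because the only reminders the protocol describes are the weekly texts for intervention compliance.
2. In Data Collection, state that the EPDS comes first at T1 and T2. If Appendix E or L already fixes the order, refer to it.
3. In Planned Analyses, state that any completed EPDS counts in the primary analysis whatever follows it, and flag EPDS-only responders.
4. Risks to Participants places the EPDS alert at the end of the questionnaire. That passage must be reconciled with an EPDS that is completed first or alone.

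Cost: one REDCap form, an ordering setting and a short amendment; the system and the blinded telephone assistants are already in place. Downside: EPDS-only women give no secondary outcomes, and a few may wait for the short form. Offering it only after the normal contacts limits this.
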